In Norway approximately 9,000 persons are operated every year for a fracture of the proximal femur. Of these, 38% are displaced femoral neck fractures(1). The mortality rate is approximately 25% the first year(2-5). Hemiarthroplasty is a universally accepted method for the treatment of displaced femoral neck fractures in patients over 70 years (6, 7). Several studies have compared the posterior approach to either anterior or lateral approach, and dislocation is often the primary outcome(8). Due to the risk of dislocation following the posterior approach, there is increased popularity of the muscle preserving approaches(9). Concerns about component positioning is relevant because for limited exposure(10, 11). In total hip replacement, geometrical restoration of leg length and femoral offset is important for patient satisfaction and postoperative function. These patients often perceives leg length discrepancy of 10mm(12) and a 15% reduction of offset is associated with increased frequency of gate disorders(12). A decrease in femoral offset can cause impaired function in terms of reduced abduction strength(13), induce instability(12) and a limp(14). Valgus/varus position may influence early loosening, especially in cemented stems, the reports on cementless stems is varying (15). Surgical approach is expected to effect the clinical outcome in this fragile population(8). In the current literature, lateral- and anterior approaches have comparable results. The effect of hemiarthroplasties inserted through the muscle preserving approach on femoral neck fractures is still unclear, but may be beneficial in terms of less pain and earlier mobilisation (9, 16-18).

Heterotopic ossification (HO) is a common complication following total hip arthroplasty, the incidence vary widely in the literature(19) and surgical approach is shown to affect the incidence(20). The Brooker classification is the most widely used grading system(21). For most patients the presence of HO is not clinically significant, but it may correlate with limitations in range of motion. Kocic et al found that only higher grades of HO is related to poorer clinical outcome(22). HO is possibly less common in cementless hemiarthroplasty. Corrigan et al found that the overall rates of HO in hemiarthroplasty patients did not vary with the surgical approach, but in patients who develop HO, the anterior and anterolateral approaches is associated with higher ossification rates.

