Is there a difference in component positioning or heterotopic ossification in uncemented hemiarthroplasty operated in lateral (Hardinge) or anterolateral (modified Watson-Jones/Röttinger) approach?

In this study we wanted to compare the radiological features and stem positioning in two well described approaches operated by experienced surgeons. Experienced surgeons defined as having done more than 50 arthroplasties for each approach, hopefully minimizing poorer results due to longer learning curve and restricted visibility in the modified Watson-Jones approach (23).

In our study we defined leg length as the perpendicular distance between a horizontal line passing through the lower edge of the teardrop to the ipsilateral center of the femoral head(24).

Femoral offset/Global offset was defined according to Lecerf et al as the distance between the longitudinal axis of the femur to the centre of the femoral head and the distance from the centre of the femoral head to a perpendicular line passing through the medial edge of the teardrop(25).

Valgus/varus position was measured on the AP and lateral view in relation to the femoral axis.

Canal fill ratio was evaluated at the following points; 2 cm above the lower trochanter, at the tip of the lower trochanter, 2 cm and 7 cm below the tip of lesser trochanter(26).

Heterotopic ossification was classified as type 1-4 according to Brooker classification(27).

The proximal femur morphology evaluated by canal flare index(CFI)(28), Dorr classification(29) and cortical thickness index (CTI)(30). CFI defined as the ratio of the intracortical width of the femur at 20 mm proximal to the tip of lesser trochanter and isthmus at 10 cm distally. CTI defined as the ratio of cortical width minus endosteal width, to cortical width at 10 cm below the tip of lesser trochanter.

Two of the authors blinded to the surgical approach do the radiological measurement.

Primary outcome:

Leg length

Secondary outcome:

Femoral offset

Valgus/Varus position

Canal fill ratio

Heterotopic ossification

Canal flare index

Dorr classification

Cortical thickness index

Radiographic evaluation:

Included an AP view of the pelvis and lateral view of the hip. The parameters was measured on pre and post operative x-rays, and at 12 months postoperative.

Inclusion/Exclusion criteria:

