In addition to the existing criteria defined in the original protocol, we excluded patients with arthroplasty, history of fracture or fracture implants in the contralateral hip.

The handling and analysis of data

The data is entered into the statistical program SPSS (SPSS Inc, Chicago, Illinois).

Sample size and and power calculation:

Based on the sample size and power calculation already done in the primary project. The sample size would be sufficient to detect a mean difference between two groups of approximately half their SD, both continuous and normally distributed outcome variables with a statistical power of 80%.

Statistical method:

Data were examined for normal distribution using histograms, Q-Q plots and the Shapiro-Wilks test. The groups were compared with the Student's independent samples t-test for continuous data, whereas categorical variables were analyzed using Pearson's chi-square test. The Student's paired samples t-test was conducted to compare changes from baseline to follow-ups. The Wilcoxon signed-rank test / Mann-Whitney U-test was performed when the normal distribution- assumptions of the Student's t-test were not met. The strength of the association between primary and secondary continuous outcomes was assessed with the Pearson correlation coefficient. Binary outcomes were assessed using logistic regression or Pearson Chi-Square test. We plan to do an intraclass correlation analysis on the measured results and a Bland-Altman plot. We plan to perform several sensitivity analysis to assess the robustness of our results and possibly do a correction for repeated measurements.

A p-value of < 0.05 was considered statistically significant. We used IBM SPSS Statistics version 25 for Windows. All statistical analysis was conducted using IBM SPSS statistics 21 for Windows (SPSS Inc., Chicago, Illinois).

Ethics

The trial was approved by the regional ethics committee Regional Committees for Medical and Health Research Ethics (REC) and registered with ClinicalTrials.gov. The trial was reported based on the guidelines of the CONSORT Statement(31) and in compliance with the Helsinki Declaration. Informed consent was obtained from all individual participants included in the study.

Publication:

Results will be published in international Orthopaedic journals with referee evaluation.

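### Leg length and femoral offset are one-hip distances compared without adjustment; the plan does not say which value is tested, and no stated analysis uses the contralateral hip

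*Combined protocol and SAP*

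**What the plan says.** The outcome definitions in the combined protocol and SAP give leg length, the primary outcome, as the "perpendicular distance between a horizontal line passing through the lower edge of the teardrop to the ipsilateral center of the femoral head". Femoral offset is "the distance between the longitudinal axis of the femur to the centre of the femoral head". Global offset adds the distance from the head centre to a line at the teardrop. Each is measured on one hip; none is defined as a difference from, or a ratio to, the other side.

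Under Statistical method, continuous outcomes are compared between arms by the "independent samples t-test for continuous data", with Mann-Whitney U as the fallback. No covariate is named. A paired test is planned for change over time, logistic regression is mentioned for binary outcomes only, and the content of the sensitivity analyses is not given.

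The other hip is mentioned once, under Inclusion/Exclusion criteria: "we excluded patients with arthroplasty, history of fracture or fracture implants in the contralateral hip". On imaging, Radiographic evaluation says: "Included an AP view of the pelvis and lateral view of the hip". On timing it says: "The parameters was measured on pre and post operative x-rays, and at 12 months postoperative". Neither the outcome list nor the statistical section says which film supplies the value for the primary comparison.

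**The concern.** Three things are left open: the variable tested (raw one-hip value, change, or side difference), the film, and the role of the contralateral hip.

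If the definition is applied literally, a patient with a large pelvis and femur has a large value whatever the surgeon did. That variation between patients widens the confidence interval. The stated hypothesis is of no difference, so a wide interval that includes zero is easily read as support for it.

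Interpretation also suffers. The Background gives the clinical motive: "In total hip replacement, geometrical restoration of leg length and femoral offset is important for patient satisfaction and postoperative function". The two thresholds that it cites, a 10 mm leg-length discrepancy and a 15% loss of offset, both need a reference. A mean one-hip distance in each arm supplies none. The operated side's own pre-operative value is a poor substitute, because that hip has a displaced femoral neck fracture when the film is taken.

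**Working it through.** **Inputs from the documents.** Detectable difference about 0.5 SD, power 80%, significance level 0.05 (Sample size and power calculation; Statistical method).

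**Assumptions.** Two-sided test; 1:1 allocation; equal SD on the two sides; a true difference that affects only the operated hip; and a correlation r between the operated and contralateral measurements. The documents give no N, no SD in mm and no r, so r is shown over a range.

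**Step 1: the plan's own figure.** The difference detectable at 80% power is very nearly (t₀.₉₇₅ + t₀.₈) × k × √(2/n), where k is the error SD relative to the one-hip SD. Unadjusted, k = 1. With n = 64 per arm (126 df): (1.979 + 0.844) × √(2/64) = 2.823 × 0.1768 = 0.499 SD. The exact noncentral-t calculation gives power of 80.1% at 0.5 SD with 64 per arm and 79.5% with 63. The half-SD statement therefore corresponds to about 64 per arm. This is implied; the documents state no N to check it against.

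**Step 2: using the contralateral hip.** For ANCOVA with the contralateral value as covariate, k = √(1 − r²), with one fewer degree of freedom. For a simple operated-minus-contralateral difference, k = √(2(1 − r)). Each detectable difference below is about 0.499 × k, checked with the noncentral t.

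| Assumed r | k, ANCOVA | Detectable, ANCOVA (SD) | k, side difference | Detectable, side difference (SD) |
|---|---|---|---|---|
| 0.1 | 0.995 | 0.497 | 1.342 | 0.670 |
| 0.2 | 0.980 | 0.489 | 1.265 | 0.631 |
| 0.3 | 0.954 | 0.476 | 1.183 | 0.591 |
| 0.5 | 0.866 | 0.432 | 1.000 | 0.499 |
| 0.7 | 0.714 | 0.356 | 0.775 | 0.387 |
| 0.8 | 0.600 | 0.299 | 0.632 | 0.316 |
| 0.9 | 0.436 | 0.218 | 0.447 | 0.223 |

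**Step 3: reading the table.** Against the raw value (0.499 SD), ANCOVA gains almost nothing at r = 0.1 to 0.3 and a good deal from 0.7 upwards. The side difference is worse than the raw value below r = 0.5, equal to it at 0.5 and better above. Apart from the one degree of freedom, ANCOVA loses to neither at any r.

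**The case against.** The strongest reply is that the plan is silent, not wrong. The contralateral exclusion makes most sense if the other hip was to be the reference. The AP pelvis view provides that hip, and the source cited for the leg-length definition is, by its title in the reference list, about limb-length discrepancy. If a side difference was always intended, anatomy is already largely removed and ANCOVA adds little at high correlation: 0.356 against 0.387 SD at r = 0.7, and 0.218 against 0.223 SD at r = 0.9. Its advantage is large only at low correlation (0.476 against 0.591 SD at r = 0.3). This stands. The loss of precision is therefore conditional on the one-hip value being tested as defined.

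The relevant r is also between an implanted hip and a native one, so it includes placement error. No document supports a value, and a low one would make the gain over the raw value slight. This stands too.

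A third reply is that precision is no help if the landmark is insensitive. The leg-length distance runs from teardrop to head centre with no femoral landmark. With the head in the native acetabulum it may change little with stem seating (reasoning from geometry; the documents do not discuss it). This stands and limits the whole leg-length analysis.

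Finally, this is an extension of a parent trial whose protocol is not among the documents. A definition there cannot be excluded.

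Some stronger readings are tempting but not supported. A reader might infer that the comparison of arms is biased; under randomisation it is not. A reader might infer that the offset outcome is undefined because two offsets are described, but the list of secondary outcomes names femoral offset only. A reader might also call it an error that a test of means cannot show greater scatter with one approach. The stated objective is to compare the measures between approaches, and comparing means is a legitimate answer to it.

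**Conclusion.** The point holds as a gap in specification with a cheap improvement available. The plan should be changed, but the validity of the randomised comparison does not depend on it. The text establishes that the outcomes are one-hip distances, that the named test is unadjusted, that the analysed quantity and film are not stated, and that no stated analysis uses the contralateral hip.

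The size is illustrative. At an implied 64 per arm, the detectable difference moves from 0.50 SD to between 0.497 and 0.218 SD for assumed correlations of 0.1 to 0.9. That gain applies if the raw value is tested. The documents do not support saying that the plan certainly wastes this precision, because they do not say that the raw value is the one tested. If it is, the result also cannot be set against the thresholds in the Background.

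**What to change.** 1. **Name the film and the model.** State one time point. The first post-operative film loses fewest patients, in a population for which the Background says: "The mortality rate is approximately 25% the first year". Compare leg length and femoral offset between arms by ANCOVA, with the same measurement on the contralateral hip, from the same AP pelvis film, as covariate. Report the adjusted difference with its 95% CI.
2. **Check the landmark first.** Before relying on any leg-length result, including the ANCOVA, confirm that the teardrop-to-head-centre distance responds to stem position. If it does not, say so; a narrower interval near zero must then not be read as evidence of equal leg length.
3. **Optional and descriptive.** Report the absolute operated-minus-contralateral difference for leg length and femoral offset, and the proportion of patients with femoral offset more than 15% below the contralateral side. Note that the Background gives the 15% figure for total hip replacement, not hemiarthroplasty.

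**Cost.** Two extra measurements (leg length and offset) on each existing film, by each of the two blinded readers already planned, plus revised wording. No new patients, visits or films. The plan is written partly in the past tense; if analysis has begun, label the adjusted analysis as added later.

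### Leg length is defined on one hip and the arms are compared only on location, so neither side-to-side discrepancy nor scatter is measured: a cheap improvement

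*Combined protocol and SAP*

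**What the plan says.** **Outcome.** The definitions that follow the research question measure leg length perpendicularly from a horizontal line at the "lower edge of the teardrop to the ipsilateral center of the femoral head". Leg length is the only primary outcome. Femoral/global offset is defined separately and does use the femoral axis. For stem alignment, "Valgus/varus position was measured on the AP and lateral view in relation to the femoral axis"; the plan does not say whether it is analysed in degrees or in categories.

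**Reference side.** The contralateral hip appears once, under Inclusion/Exclusion criteria: "we excluded patients with arthroplasty, history of fracture or fracture implants in the contralateral hip". No outcome is defined as a difference between sides. The films, under Radiographic evaluation, "Included an AP view of the pelvis and lateral view of the hip", taken before and after surgery and at 12 months.

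**Analysis.** Under Statistical method, the arms are compared by the "independent samples t-test for continuous data, whereas categorical variables were analyzed using" the chi-square test, or by Mann-Whitney where normality fails. Paired tests address change from baseline. The criterion is "A p-value of < 0.05 was considered statistically significant". The section names no confidence interval; the Ethics section refers to CONSORT for reporting.

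**Motivation.** The Background refers to limited exposure, to geometrical restoration, to a perceptible discrepancy of 10 mm and to a 15% loss of offset, the last three in the context of total hip replacement. The text after the research question gives "restricted visibility in the modified Watson-Jones approach" as a reason for using experienced surgeons.

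**The concern.** There are two gaps between the motive and the measurement.

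First, restoration and discrepancy are relative to a target, usually the other hip. The leg-length distance has no target. It also stops at the head centre, so it contains no point on the femur; a change in the level of the femur relative to the head need not show in it. Two analysts could derive different primary variables from this text. This part needs no assumed numbers.

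Second, restricted exposure could plausibly make positioning less consistent as well as shift its average. The planned tests respond to a shift. If one approach gave more hips that were too long and also more that were too short, the signed values would cancel and the tests would be nearly blind to it.

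**Working it through.** **1. Inputs.** From the documents: 80% power to "detect a mean difference between two groups of approximately half their SD" (Sample size and power calculation), and about 25% first-year mortality (Background). Assumed: two-sided 5%, 1:1 allocation, normal data, and every SD in mm.

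**2. Sample size implied by the power statement.** n per arm = 2(1.96 + 0.84)² / 0.5² ≈ 63 by the normal approximation. With the t distribution it is 63.8, so 64, with power 80.1%. The documents state no N to check this against. For 12-month films, 64 × (1 − 0.25) = 48 per arm is used as a lower case.

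**3. Definition against motive.**

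| The Background is concerned with | The plan measures |
|---|---|
| Restoration of leg length, discrepancy between sides | Distance on one hip, no target, no femoral point |
| 15% reduction of offset | Offset, with no stated reference for the reduction |
| Positioning under limited exposure | Location of each measure by arm |

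The pre-operative film does not supply the target for the operated side, because it shows the fractured hip.

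**4. What a location test misses.** Suppose the operated-minus-contralateral discrepancy has mean 0 in both arms, with SDs of 5 and 8 mm. The share of hips beyond 10 mm is 2[1 − Φ(10/5)] = 4.6% against 2[1 − Φ(10/8)] = 21.1%. The mean difference is zero, so the t-test rejects at about its nominal level.

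**5. Simulated rejection rates** (6,000 runs; ranges cover 48 to 64 per arm).

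| SDs (mm) | Planned t-test or Mann-Whitney | Mann-Whitney on absolute values | Same, both arms shifted 3 mm | Brown-Forsythe on signed values, with or without the shift |
|---|---|---|---|---|
| 5 v 6 | about 5% | 17-20% | 11-14% | up to about 25% |
| 5 v 7 | about 5% | 41-56% | 29-35% | 53-68% |
| 5 v 8 | about 5% | 69-82% | 51-63% | 81-92% |

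For 6 v 7 and 7 v 8 mm, without the shift, the absolute-value test rejects 13-15% and 11-14%. With equal SDs of 5 mm it rejects about 5%, as it should. Brown-Forsythe centres each arm on its own median, so it needs no target and a shared shift does not affect it. Fisher's exact test on hips beyond 10 mm rejects 6-10%, 27-42% and 58-76% for the three rows of the table, less than either alternative.

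**6. Why the signed test must stay.** For a pure 3 mm shift at SD 6 mm, the t-test rejects 68-79% and the absolute-value test 10-11%.

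**7. Cost in false positives.** For k independent extra tests at 5%, the chance of at least one is 1 − 0.95^k: 9.75% for two, 14.3% for three, 18.5% for four.

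**8. Interval.** The 95% half-width is t × √(2/n): 1.979 × √(2/64) = 0.350 SD, and 1.986 × √(2/48) = 0.405 SD. At 64 per arm, an observed difference between 0.15 and 0.35 SD would be non-significant while 0.5 SD stayed inside the interval.

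**The case against.** The stated question is whether positioning differs, not which approach is more accurate, and a signed comparison answers it. The requirement of more than 50 arthroplasties per approach makes a large difference in spread less likely, and for small differences no test proposed here has useful power. The contralateral exclusion, the pelvic film and the word ipsilateral all point to an intended comparison of sides. The N is inferred. If the original sizing already allowed for deaths, 48 per arm counts them twice. Absolute deviation also mixes bias with spread.

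Most of this stands, and it limits the point to an improvement. It does not supply the missing definition: an implied reference side is not a stated one, and subtracting the other side does not by itself add a femoral landmark.

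A reader might infer more than the documents support:

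- *That the missing confidence interval is a serious defect, or that equivalence will be claimed from p > 0.05.* The plan sets no margin, claims no equivalence and refers to CONSORT for reporting. The interval is a minor wording point.
- *That a difference in scatter would never lead to the comparison with clinical findings.* The main objective makes that step depend on a difference existing, without defining this as a significant mean difference.
- *That no contralateral comparison was intended, or that one approach is less consistent.* The exclusion suggests the opposite of the first, and nothing in the documents shows the second.

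**Conclusion.** The point holds as a cheap improvement. The primary outcome as defined does not measure side-to-side discrepancy, and the between-arm tests reject only about 5% when the approaches differ in scatter alone. The definitional part rests on the text and needs no assumption. The size of the gain from looking at scatter is conditional: substantial at 5 versus 8 mm, small at 5 versus 6 mm (about 17-25% rejection across the absolute-value and Brown-Forsythe tests, without a shared shift). All SDs, 64 per arm and 48 per arm are assumptions, as is a normally distributed discrepancy that the plan does not yet define. The original trial's protocol was not available and may say more.

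**What to change.** 1. Define leg length and offset for analysis as operated minus contralateral hip, measured on the pelvic AP films already planned. Confirm that the leg-length distance includes a femoral landmark, so that it reflects leg length.
2. Keep the signed comparison between approaches as the primary analysis.
3. Add, labelled as exploratory secondary outcomes, absolute leg-length discrepancy and, if valgus/varus is recorded in degrees, its absolute deviation. If consistency itself is the question, add a Brown-Forsythe test on the signed values.
4. Report proportions beyond 10 mm or with more than 15% offset loss descriptively only, noting that the Background gives these thresholds for total hip replacement.
5. As a minor wording change, report the between-approach difference with its 95% confidence interval (Hodges-Lehmann where Mann-Whitney is used).

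The cost is some SAP wording, contralateral measurements with no new imaging or patients, and a few unadjusted exploratory tests with the false-positive risk shown in step 7 of the working.

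### The test for leg length and every other continuous outcome is chosen after a look at the data, so the primary test and what it estimates are not fixed in advance, and no unequal-variance method is named

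*Combined protocol and SAP*

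**What the plan says.** All of this is in the protocol's section on handling and analysis of data, mainly under Statistical method.

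- **Check:** "Data were examined for normal distribution using histograms, Q-Q plots and the Shapiro-Wilks test". No cut-off is given. The text does not say whether normality is judged per arm, pooled or at each visit, or what happens if the plots and the test disagree.
- **Default:** "The groups were compared with the Student's independent samples t-test for continuous data".
- **Fallback:** "The Wilcoxon signed-rank test / Mann-Whitney U-test was performed when the normal distribution- assumptions of the Student's t-test were not met".
- **Threshold:** "A p-value of < 0.05 was considered statistically significant". Sidedness is not stated.
- **Power:** the sample is said to be "sufficient to detect a mean difference between two groups of approximately half their SD", at 80% power, for normally distributed outcomes. No number of patients, allocation ratio or SD in millimetres is given; these are deferred to the primary project.

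Leg length is the only primary outcome and has no test rule of its own. Sensitivity analyses are promised but not described. No unequal-variance test and no effect estimate with a confidence interval is named.

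**The concern.** A primary analysis should be settled before outcome data are seen. Here it depends on a check that is partly visual, so two analysts following the plan could report different primary tests from the same measurements.

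The two tests also answer different questions. Student's t-test compares means, which is what the power statement refers to. Mann-Whitney compares the rank order of two samples. If the arms differ in spread or shape, it is not a test of equal means, and it gives little weight to how far out an extreme value lies.

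The default has a limit of its own. Student's t-test pools the variance, which is what the name means although the plan does not spell it out. Its error rate is off when arms differ in both size and spread. Equal arm sizes at analysis cannot be assumed: patients with contralateral arthroplasty, fracture or implants are excluded, and the Background gives first-year mortality of about 25%.

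**Working it through.** **1. The plan's own figure.** No sample size is stated, so I back-solve it, assuming a two-sided 5% level. n per arm = 2(1.960 + 0.842)² / 0.5² = 62.8, so 63; the exact t-test gives 63.8, so 64. If 25% are lost by 12 months, 64 × 0.75 = 48 remain, with 67.9% power at half an SD. I use 48 per arm below. Postoperative films would be nearer 64.

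**2. Assumptions.** SD ratios, outlier share and direction, skewness, arm sizes and the Shapiro-Wilk cut-off are not in the documents. The rule is modelled as: p < 0.05 in either arm leads to Mann-Whitney, otherwise Student's t-test. Percentages are simulated unless a formula is shown.

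**3. Unequal arms and unequal SDs, normal data (54 v 42, SDs 1 and 2).** Compare the pooled squared standard error with the true one.
- Smaller arm more variable: pooled variance (53×1 + 41×4)/94 = 2.309. Pooled SE² = 2.309 × (1/54 + 1/42) = 0.0977; true 1/54 + 4/42 = 0.1138. The critical value 1.986 acts as 1.986 × √(0.0977/0.1138) = 1.84, a size of about 6.6%.
- Larger arm more variable: pooled variance (53×4 + 41×1)/94 = 2.691. Pooled SE² = 0.1139; true 4/54 + 1/42 = 0.0979. The critical value acts as 2.14, a size of about 3.2%.
- Simulation gives about 7% and 3 to 4%; Welch gives about 5%.

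**4. Equal arms, unequal SDs, normal data.** Pooled SE² = [(s₁² + s₂²)/2] × (2/n) = (s₁² + s₂²)/n, which is the true value. The distortion in step 3 vanishes. Simulated type I error of the rule at 63 per arm is 5.1% (SD ratio 1.5) and 5.6% (ratio 2). Power falls because the SD is larger, and Welch recovers none of it (57% v 57%, 42% v 42%).

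**5. Skewed data with equal means and unequal spread (gamma, skewness 1.4; 48 per arm).** Mann-Whitney rejects in about 12% of trials at SD ratio 1.5 and 20% at ratio 2; Welch rejects in about 5%.

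**6. Stems displaced to one side (15% of one arm moved by 3 or 4 SD; 48 per arm).**
- Mean comparison: the mean shift is 0.15×3 = 0.45 or 0.15×4 = 0.60. The affected arm's variance is 1 + 0.15×0.85×9 = 2.15, or 1 + 0.15×0.85×16 = 3.04. The noncentrality is 0.45/√(3.15/48) = 1.76, or 0.60/√(4.04/48) = 2.07. Power is about Φ(1.76 − 1.99) = 41%, or Φ(2.07 − 1.99) = 53%.
- Rank comparison: the probability that a patient in that arm exceeds one in the other is 0.85×0.5 + 0.15×Φ(3/√2) = 0.572, or 0.575 at 4 SD. The null SE is √(97/(12×48×48)) = 0.0592, so z is 1.22 or 1.26 and power about 23 to 24%.
- Simulation gives 38 to 54% for the mean comparison and 24 to 30% for the rule.

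**7. Cases where ranks do better (half-SD effect, 48 per arm).**
- Skewed data, pure shift: Mann-Whitney 82%, mean comparison 68%.
- 15% outliers at 4 SD in both directions in one arm: rule 50%, Welch 37%. Type I error of the rule stays at 5 to 6%.

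**8. Cost of Welch where Student's test is ideal.** Normal data, equal SDs, half-SD effect, 48 per arm: Welch 67.2%, Student 67.3%.

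**9. How much the choice can matter.** At a half-SD effect with 48 per arm, the t-test and Mann-Whitney disagree on significance in about 7% (normal) to 15% (skewed) of trials.

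**The case against.** The strongest reply is that the rule is common and does no harm in the setting for which power is stated. With normal data, equal SDs and 63 per arm, it has 5.0% type I error and 79.7% power. That stands.

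A reader might infer that the rule does worst whenever one approach has more scatter or a few badly placed stems. The documents do not support that. Step 4 shows that scatter alone leaves the error rate intact. Step 7 shows that outliers falling both ways favour the rule, and leg length can err long or short. No malposition rate, size or direction is given.

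Nor does the plan predict unequal spread. The Background calls positioning a relevant concern with limited exposure. The study description then offers a mitigation: every surgeon has done more than 50 arthroplasties by each approach. The hypothesis is no difference in component positioning.

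Two further points have weight. The rejections in step 5 are false positives only if the null is equal means, since the distributions do differ; the hypothesis is not worded in means, though the power statement is. Also, the plan's check includes histograms and Q-Q plots, so the modelled Shapiro-Wilk rule is a stand-in for it.

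None of this fixes the primary test in advance. The promised sensitivity analyses do not either, because they are not specified.

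**Conclusion.** The point holds in a limited form. By the plan's own text, the primary test and its estimand depend on the data, while power is stated for a mean difference and no unequal-variance method is named.

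The numerical consequences are conditional. Student's test is off by about two percentage points either way, but only if arms differ in both size and SD. Rejection of equal means at 12 to 20% needs skewness together with unequal spread. The drop in power to about a quarter, from 38 to 54%, needs a one-sided minority of displaced stems in one arm. Each rests on assumed values. The claim that the rule fails under greater scatter or malposition in general should not be made. This is a cheap improvement of low to moderate priority.

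**What to change.** Replace the test-selection sentences for between-arm comparisons with wording such as: *Continuous outcomes, including leg length, are compared between approaches by the difference in means with a 95% confidence interval, using Welch's t-test (the row for equal variances not assumed in SPSS). No test of normality or variance decides the method. Mann-Whitney is reported for every continuous outcome as a sensitivity analysis.* Histograms and Q-Q plots stay as description.

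The cost is one edit to the plan and no new software, since SPSS prints the Welch row by default. Power is essentially unchanged when the data are normal with equal SDs (step 8). The downside should be stated openly: the rank test is stronger when skewed data are simply shifted, and the present rule is stronger when outliers fall in both directions (step 7). Reporting Mann-Whitney every time keeps that information visible. The two tests may still disagree, but which one is primary will have been settled beforehand.
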